2.6.2 Potential Benefits

The primary benefit for this study will be to improve access to 5-FC for patients in greatest need of this therapy. It is hoped that lower doses of 5-FC will be equally effective compared to the traditional dosing, which will reduce the cost of therapy for individual patients and eventually HIV care programs. A secondary benefit by participating in the study is that the lower doses may be associated with lower toxicities hence providing data to recommend decreasing costs of safety monitoring in the long term. High doses of 5-FC are associated with leukopenia, thrombocytopenia and acute renal injury, especially when used in conjunction with IV AMB. Lower doses of 5-FC will likely have reduced burden of side effects on individual patients.

Participants will receive scheduled lumbar punctures at baseline, Day 3 ± 1 , Day 7 ± 2 , and Day 14 ± 2 and additionally as required for control of intracranial pressure and documentation of CSF sterilization. Receipt during the first week of at least one therapeutic lumbar puncture with control of intracranial pressure has a 69% relative reduction in 10 day mortality in Uganda.⁵² Thus participants will likely benefit from study participation through receipt of scheduled lumbar punctures with control of intracranial pressure.

There is the potential benefit of access to single high dose liposomal AMB, which has recently been shown to be as effective as the 7-day course of IV AMB deoxycholate. When available to the study team, liposomal AMB will be used which will also reduce incidence of side effects related to AMB deoxycholate.

3. OBJECTIVES

3.1 Study Objectives

3.1.1 Phase II Trial Objective

To demonstrate the reduced dose of 5-FC, when combined with IV AMB for induction therapy of CM is non-inferior compared to traditional dosing of 5-FC in reducing fungal burden of *Cryptococcus*

3.1.2 Phase II Secondary Objective

- To determine if there remains a mortality benefit to 5-FC for induction therapy at reduced dosing.
- To assess the overall safety and tolerability of 5-FC at reduced dosing.

3.2 Study Outcome Measures

Primary Endpoint

1. CSF culture clearance at 2 weeks (Early Fungicidal Activity, or EFA: change of \log_{10} *Cryptococcus* CFU/mL CSF/day as measured by serial quantitative CSF fungal cultures)

Key Secondary Endpoint

1. Desirability of Outcome Response (DOOR) as ordinal ranked maximum score tested by Win Ratio.
 - a. 18-week Survival with CSF sterility by 2-weeks
 - b. 18-week survival with CSF culture positivity beyond 2 weeks
 - c. Grade 3 hematological adverse event by 2 weeks
 - d. Grade 4 hematological adverse event by 2 weeks
 - e. Lost to follow up before 18-weeks
 - f. Serious Adverse Event through 18 weeks (e.g. all-cause re-hospitalization, permanent neurologic deficit)
 - g. Death by 18-weeks

Secondary Endpoints

1. CSF culture sterility cumulative incidence over 18 weeks
2. 18-week survival time

[figure not shown]
Safety & Exploratory Endpoints

1. Incidence of Grade 3-5 abnormal laboratory test results (as per the NIAID DAIDS toxicity grading scale) through Week 2 of the study
2. Incidence of clinical Adverse Events (Grade 3-5) or SAEs through week 2
3. Pharmacokinetics of 5-FC concentrations in blood, CSF, and other tissues.

4. STUDY DESIGN

4.1 Phase II Study Design

Figure 4.1

This is a single-arm trial with historical controls to compare the efficacy and safety of reduced dosing of 5-FC induction therapy for the treatment of cryptococcal meningitis in combination with IV AMB to standard of care, with EFA as the primary endpoint.

Participants will be enrolled into an investigational cohort at study entry.

1. The investigational cohort will receive 60mg/kg/day of 5-FC divided into 3 doses per day for 10 days, n~50 total enrolled to achieve n=36 CSF culture positive.
2. The control group will consist of historical participants in the AMBITION trial
3. All participants will receive liposomal Amphotericin B 10 mg/kg, single-dose infusion, if available.
4. If liposomal Amphotericin is unavailable, participants will receive IV amphotericin deoxycholate 0.7-1.0 mg/kg/day for 7 days.
5. All participants will receive fluconazole 1200 mg/day during induction therapy from day 1 to 14 then consolidation therapy 800 mg/day from day 15 to 10 weeks, and maintenance therapy of 200 mg/day after 10 weeks.
6. All participants will receive lumbar punctures at diagnosis, day 3, day 5-7, day 10-14, and additionally as required for control of intracranial pressure and documentation of CSF sterilization. Therapeutic LPs conducted during the first week have a ~70% relative survival benefit.

Investigational cohort will receive:

- IV Amphotericin B deoxycholate 1 mg/kg/day for 7 days or IV Liposomal Amphotericin B 10mg/kg single dose.
- Oral flucytosine (5FC) 60mg/kg/day for 10 days in 3 divided doses
- Oral fluconazole 1200mg/day from Day 1 to 14
- Oral fluconazole 800mg/day from Day 15 to Week 10
- Oral fluconazole 200mg/day thereafter

The control cohort will be drawn from the AMBITION trial that was conducted partly in Uganda.⁴³ This was a randomized clinical trial that evaluated single high-dose amphotericin B (10 mg/kg) with fluconazole (1200 mg/day) and flucytosine (100 mg/kg/day) for 2-week induction therapy of cryptococcal meningitis compared to standard amphotericin deoxycholate (1 mg/kg/day) with flucytosine (100 mg/kg/day). The trial enrolled participants who were HIV positive with a first episode of cryptococcal meningitis diagnosed by cryptococcal antigen or India ink staining. Participants were excluded if they were pregnant, had already taken amphotericin or fluconazole for >48 hours, had a previous serious reaction to the study medications or were taking a medication that would be contraindicated with the study medications. In Uganda, the trial enrolled 163 participants in the control arm and 164 in the intervention arm for a total enrollment of 327 Ugandan participants. The control cohort will be drawn from Ugandan participants. If IV liposomal amphotericin B is used in the investigational cohort then they will be drawn from the intervention arm. If IV deoxycholate amphotericin B is used in the investigational cohort then they will be drawn from the control arm. We will compare the EFA of all the control participants to the interventional participants using multivariate mixed linear regression, adjusting for confounding factors such as CD4+ count, GCS<15 or not, prior exposure to ART or not and other important clinical factors. We will also compare 10-week survival in the

interventional and control cohorts, using multivariate Cox regression, adjusting for the same clinical factors as the mixed regression model.

This 2018 and 2022 WHO recommended regimen is based on a phase III randomized clinical trial demonstrating that:

- i) 1 week of IV AMB had equivalent survival as 2 weeks of IV AMB;²
- ii) 1 week of IV AMB combination therapy was less toxic than 2 weeks of IV AMB;² and
- iii) Adjunctive flucytosine had superior survival to adjunctive fluconazole.²

A DSMB review by the full committee will occur after 10 participants have been enrolled with >2 weeks of accrued data. A local Ugandan community member will be invited to attend open DSMB meetings. The DSMB safety reports will be submitted to the IRBs and regulatory authorities.

Timing of ART Initiation or Switch.

ART will be initiated for ART-naïve participants ~6 weeks after CM diagnosis, per current standard of care.²⁵ Persons enrolled with a failing ART regimen will be switched to 2nd line HIV therapy at ~6 weeks while persons who have initiated ART in the preceding 2 weeks will have their ART interrupted and re-initiated ~6 weeks after CM diagnosis, in accordance with consensus best practices.⁵³ ART management decisions for persons on ART longer than 2 weeks will be at investigators' discretion. Outpatient visits will occur every 2-4 weeks at the study site outpatient HIV clinic until the conclusion of the study at 18 weeks. Patients can elect to continue to receive routine HIV care at the site after study completion. If persons have active cryptococcal-related issues (e.g. IRIS or relapse) ongoing at 18 weeks, the participant will continue to be followed by the study team until their condition has stabilized.

Prior published outcome data suggest no overall difference in 18-week survival between those who present ART-naïve vs. ART-experienced on a failing regimen.⁵¹

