Prelim Data	
Molloy et al. demonstrated in the ACTA trial published in 2018 that 1 week of IV Amphotericin B 1 mg/kg plus oral 5-FC 100 mg/kg is the optimal management for the first week of CM. These are shown to have benefits in mortality and similar rates of fungal clearance from the CSF to other combination regimens.

Phase II Study Design	
Prospective, open-label trial to compare the efficacy and safety of lower doses of 5FC during induction therapy to historical controls with standard 5FC dosing.
 
 1. Participants in the trial will receive 60mg/kg/day of 5-FC in 3 divided doses for 10 days, n=36 2. Single-dose liposomal amphotericin (10mg/kg) is preferred, if available. 3. Amphotericin B 0.7-1.0 mg/kg/day may be used if needed. 4. Historical controls drawn from the AMBITION trial will be used as a comparison group, selected weighted by inclusion/exclusion criteria, baseline characteristics and therapies received. Induction therapy for control group participants followed the 2018 WHO cryptococcal guidelines with 7 days of 5-FC 100mg/kg/day and 7 days of IV Amphotericin deoxycholate followed by 1200mg fluconazole/day for 7 days. The intervention group received single-dose liposomal amphotericin plus 5-FC and fluconazole 1200 mg/day.

	
All participants will receive fluconazole 1200mg/day during consolidation therapy from day 1 to 14 then 800mg/day from day 15 to 10 weeks, and 200mg/day after 10 weeks.
 
All participants will receive lumbar punctures at diagnosis, day 3, day 5-7, day 10-14, and additionally as required for control of intracranial pressure and documentation of CSF sterilization. Controls from Ambition will be matched for the same LP windows. Therapeutic LPs conducted during the first week have a ~70% relative survival benefit.

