Phase II Study Drug and Dosing	
 • Participants will receive 5-FC 60mg/kg/day for 10 days. • Participants will receive IV AMB 0.7-1.0 mg/kg/day for 7 days. • Liposomal Amphotericin B single IV dose 10 mg/kg is preferred, when available. • All participants will receive fluconazole 1200 mg/day during consolidation therapy from day 1 to 14 then 800 mg/day from day 15 to 10 weeks, and 200mg/day after 10 weeks.
Phase II Monitoring	
 • All participants will have CSF quantitative fungal cultures performed on Days 1, 2-4, 5-7, and 10-14 of antifungal treatment. • 3x weekly CBC, chemistries, and kidney function tests for duration of induction therapy during hospitalization
Phase II Safety Analysis	
The Data Monitoring Committee (DMC) will conduct interim safety analysis after 10 participants are enrolled with >2 weeks of accrued data and calculable EFA.
 
EFA and culture positive Cryptococcus relapse will be monitored by the trial investigators, and if statistical evidence shows that EFA <0.2 log₁₀ CFU/mL/day, then an early DMC will be called.

Phase II Statistical Design Rationale	
Early fungicidal activity (EFA) is a quantitative measure of antimicrobial activity for an antifungal regimen in human patients with cryptococcal meningitis. In numerous trials, EFA correlates well with 10-week mortality. Specifically, EFAs worse than 0.20 log₁₀ CFU/mL/day are associated with higher mortality (>50%) and EFA better than 0.3 log₁₀ CFU/mL/day is associated with lower mortality (30-40%).
 
EFA is calculated by measuring the slope of the clearance rate of yeast from CSF, which is calculated from longitudinal quantitative CSF cultures collected over two weeks.
 
By intent to treat analysis, all participants who are enrolled in this study will be included for analysis.

Clinical Trial Sites	
 1. Mulago Hospital, Kampala, Uganda 2. Kiruddu Hospital, Kampala, Uganda 3. Mbarara Regional Referral Hospital, Mbarara, Uganda

Estimated Time to Complete Enrollment:	Up to 12 months
---	-----------------

Table of Contents

1. KEY ROLES	1
2. BACKGROUND AND SCIENTIFIC RATIONALE	2
2.1 Background Summary and Study Hypotheses	2
2.2 Burden of Cryptococcal Meningitis	2
2.3 Treatment of Cryptococcal Meningitis	4
2.4 Rationale for Optimizing 5FC Dose	6
2.5 Early Fungicidal Activity	7
2.6 Potential Risks and Benefits	10
3. OBJECTIVES	12
3.1 Study Objectives	12

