2.3 Treatment of Cryptococcal Meningitis

Standard cryptococcal meningitis treatment is divided into three phases: a 2 week induction phase, followed by an 8-week consolidation phase, and an extended maintenance phase thereafter for secondary prophylaxis.²⁴ Table 2.3 outlines the treatment recommendations for cryptococcal meningitis in HIV-infected individuals. Historically, international treatment guidelines have been informed primarily by large multisite clinical trials with endpoints of treatment success and survival at 2 weeks and 10 weeks. Ongoing mortality occurs between 10-18 weeks. After 18 weeks, approximately 90-95% will be alive at 5 years.^{23,25}

Table 2.3: 2018, 2022 WHO Antifungal Treatment Recommendations for Cryptococcal Meningitis

Medication and Dose	Week 1	Week 2	Week 3-10	Week >10
Amphotericin B (1.0 mg/kg/day) + flucytosine 100mg/kg/day	Yellow			
Fluconazole 1200mg daily		Yellow		
Fluconazole 800mg daily			Light Blue	
Fluconazole 200mg daily				Through 12 months

Treatment Phase	Induction	Induction	Consolidation	Secondary Prophylaxis
-----------------	-----------	-----------	---------------	-----------------------

These recommendations are based on a published 2018 phase III randomized trial.²⁰ This remains the 2022 recommended regimen for locations without access to liposomal amphotericin B (Ambisome®).²¹

[figure not shown]
In the published ACTA trial, one week of IV amphotericin B deoxycholate was non-inferior to two weeks of IV AMB (Figure 2.3).² The best therapy in the ACTA trial was 1 week of IV AMB + flucytosine with 24% (27/113) 10-week mortality.

Cryptococcal mortality can be reduced by the use of high-dose amphotericin B (0.7-1.0 mg/kg/day), alongside aggressive inpatient management of raised intracranial pressure.¹² In

most resource-limited settings, standard induction therapy for cryptococcosis includes the alternate regimen of IV AMB for 14 days combined with high-dose fluconazole (800-1200mg/day).

The ability of amphotericin to rapidly and consistently sterilize the cerebrospinal fluid (CSF) of cryptococcal patients suggests that amphotericin should be central to any induction strategy.²⁶

Figure 2.3: ACTA trial, comparison of induction therapies

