6.2.1.1 Amphotericin B Deoxycholate

Amphotericin B deoxycholate is available in single vials. Each vial contains a sterile, non-pyrogenic, lyophilized cake providing 50 mg amphotericin B and 41 mg sodium deoxycholate buffered with sodium phosphates. Amphotericin B is solubilized by the addition of sodium deoxycholate to form a mixture, which provides a colloidal dispersion for intravenous infusion following reconstitution.

Typical AMB deoxycholate dosing for CM is 0.7-1 mg/kg daily. Amphotericin should be administered by slow intravenous infusion over a period of approximately 4 hours. The recommended concentration for intravenous infusion is 0.1 mg/mL (1 mg/10 mL).

Acquisition: Any nationally registered, GMP-manufactured, and/or FDA-approved formulation is acceptable.

Product Storage and Stability: Prior to reconstitution, AMB deoxycholate should be stored under refrigeration 2° to 8°C (36° to 46°F) and protected against exposure to light.

Study administration for all treatment arms:

Subjects will receive the WHO standard 7-day course of IV amphotericin B deoxycholate 0.7-1.0mg/kg/day.

Amphotericin is well known for its frequent and often severe side effects, as outlined in Appendix A. Significant infusion reactions must be anticipated with a tendency toward IV-associated phlebitis. To help prevent this, IV lines will be flushed after amphotericin is administered and peripheral IV sites generally rotated at least every 3 days. With IV AMB, provide 1–2 L saline/day, along with careful monitoring for renal dysfunction and particularly electrolyte abnormalities (K and Mg). Electrolyte management with amphotericin is essential, and will follow WHO treatment guidelines including supplemental potassium and magnesium.⁵³

Guidelines for use of IV AMB and management of common toxicities associated with amphotericin B are included in the MOP and may be consulted, at the site investigator's discretion. Participants who permanently and prematurely discontinue IV AMB because of an AE will be followed closely until resolution of the AE can be documented. Those who require additional IV AMB in any arm will be tracked, as additional IV AMB is a secondary endpoint.

When not receiving IV AMB, additional IV fluids will be given as clinically indicated.

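### The deoxycholate fallback allows 0.7-1.0 mg/kg/day, while its matched AMBITION control arm is described at 1 mg/kg/day; fix the planned dose at 1 mg/kg/day

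*Combined protocol and SAP*

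**What the plan says.** Liposomal amphotericin 10 mg/kg once is the preferred backbone and matches its AMBITION arm, so this point concerns the deoxycholate fallback only.

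Four places give a range:
- Synopsis, Phase II Study Design: "Amphotericin B 0.7-1.0 mg/kg/day may be used if needed".
- Synopsis, Phase II Study Drug and Dosing: "Participants will receive IV AMB 0.7-1.0 mg/kg/day for 7 days".
- Section 4.1, item 4: "If liposomal Amphotericin is unavailable, participants will receive IV amphotericin deoxycholate 0.7-1.0 mg/kg/day for 7 days".
- Section 6.2.1.1: "Subjects will receive the WHO standard 7-day course of IV amphotericin B deoxycholate 0.7-1.0mg/kg/day".

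Other places give a single dose:
- Section 4.1, list of what the investigational cohort receives: "IV Amphotericin B deoxycholate 1 mg/kg/day for 7 days or IV Liposomal Amphotericin B 10mg/kg single dose".
- Section 2.3, Table 2.3 (WHO regimen): "Amphotericin B (1.0 mg/kg/day) + flucytosine 100mg/kg/day". Table 6.2 in section 6.1 shows the same dose.
- Section 4.1, description of AMBITION: single-dose liposomal treatment "compared to standard amphotericin deoxycholate (1 mg/kg/day) with flucytosine (100 mg/kg/day").

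Section 4.1 also fixes the comparison: "If IV deoxycholate amphotericin B is used in the investigational cohort then they will be drawn from the control arm". The synopsis gives that arm 7 days of deoxycholate. It adds that controls are weighted by, among other things, the therapies they received. Section 4.1 adjusts for CD4 count, GCS, prior ART and an open list of other clinical factors; amphotericin dose is not named.

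**The concern.** The trial has one arm and historical controls, and it is meant to show what happens when the 5-FC dose is lowered. The plan already aligns amphotericin formulation with the control arm. The range undoes part of that alignment: a fallback participant could receive less amphotericin than the control regimen as well as less 5-FC, and no rule says who receives which dose within the range.

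The consequences run in opposite directions. For EFA, less amphotericin taken alone would slow clearance, if it does anything, and could be misread as a cost of the lower 5-FC dose. For toxicity it could favour the new regimen. Section 11.3 hypothesises reduced toxicity against standard-dose 5-FC. Section 11.6 names anemia and acute kidney injury as examples within the key safety endpoint, and the DOOR in section 11.5 ranks grade 3 and 4 hematological events. Section 9.2.2 lists anemia and renal failure as common effects of IV amphotericin, and anemia under flucytosine too. Section 6.2.2 notes that renal impairment can make flucytosine accumulate, so amphotericin dose could also act through 5-FC exposure. With no concurrent arm, these contributions would be hard to separate afterwards.

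**Working it through.** The plan states no figure to reproduce. The check is arithmetic on doses.

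**Inputs.** Fallback range 0.7 to 1.0 mg/kg/day for 7 days (section 4.1, item 4). Control-arm nominal dose 1 mg/kg/day (section 4.1) for 7 days (synopsis). EFA sample 36, assumed SD 0.20 (section 11.4.1). Ugandan AMBITION liposomal arm, 164 enrolled (section 4.1).

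**Permitted gap.** Cumulative dose = daily dose × 7; shortfall = 1 − permitted/control.

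| Daily dose (mg/kg) | 7-day dose (mg/kg) | Shortfall v control |
|---|---|---|
| 0.70 | 0.70 × 7 = 4.90 | 1 − 4.90/7.00 = 30% |
| 0.85 (mid-range) | 0.85 × 7 = 5.95 | 1 − 5.95/7.00 = 15% |
| 1.00 | 1.00 × 7 = 7.00 | 0% |

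For liposomal participants the gap is zero. With the fallback planned at 1 mg/kg/day, the nominal gap is zero for everyone.

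**How many could be affected.** The fallback share is not in the documents. Assumed shares applied to 36 show the range and are not an estimate: 0% gives 0; 10% gives 3.6, about 4; 25% gives 9; 50% gives 18; 100% gives 36.

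**Can the planned analysis remove the gap?** Weighting by therapies received needs controls who had the lower dose, and no control regimen below 1 mg/kg/day is described. Adding amphotericin dose to the regression has the same weakness: on nominal dose, the deoxycholate controls all sit at one value. Neither device can clearly correct for it.

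**Precision of a liposomal-only analysis.** Unadjusted 95% half-width = 1.96 × 0.20 × √(1/n + 1/164), assuming a common SD of 0.20 and an EFA for all 164 controls:
- n = 36 (no fallback): 1.96 × 0.20 × √(0.02778 + 0.00610) = 0.072.
- n = 27 (assumed 25% fallback): 1.96 × 0.20 × √(0.03704 + 0.00610) = 0.081.

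The restriction costs little precision at that share and cannot be run if everyone is on the fallback.

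**The case against.** The case for leaving the text alone is substantial.

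- **The doses are compatible.** A site giving 1 mg/kg/day satisfies every section. Sections 2.3 and 6.2.1.1 present 0.7-1.0 mg/kg/day as established high-dose or typical practice, and allowing a customary range for a background drug is a legitimate choice. This stands: a reader might infer a contradiction between two doses, and the text does not support that. What remains is that section 6.2.1.1 calls the range the WHO standard while the protocol's own WHO tables show 1.0.
- **The fallback may never be used.** Liposomal drug is preferred, and section 6 says the study provides its medications. The remark in section 6.2.1.2 that liposomal preparations are rarely available in Africa describes the continent, not this trial's supply. This stands; the number affected could be zero.
- **For the primary endpoint the argued direction is conservative.** A reader might fear that the range makes a false non-inferiority finding easier. A lower amphotericin dose would work against non-inferiority, so that fear is not supported.
- **The toxicity analyses carry limited inference.** Section 11.1 reserves hypothesis testing for the primary efficacy endpoint and section 11.7 calls the secondary endpoints primarily descriptive. This mostly stands, although section 11.5 has the DOOR tested by win ratio.
- **Weighting and adjustment are planned,** and section 11.3 defers historical-control details to the SAP. This answers less, because no lower-dose control regimen is described.

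**Conclusion.** The point holds as a modest, inexpensive improvement. For the deoxycholate fallback only, the plan permits a dose up to 30% below the nominal dose of the controls used for comparison (4.9 v 7.0 mg/kg over 7 days), in a design meant to isolate 5-FC dose. If the fallback is used below 1 mg/kg/day, the EFA comparison would tend to be conservative, while the toxicity comparison and the DOOR could be flattered.

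Thirty percent is the permitted maximum. A reader might take it as the expected shortfall, but the documents give no distribution of doses within the range and no doses actually received in AMBITION. They also give no effect of 0.7 v 1.0 mg/kg/day on EFA or toxicity, so no size of bias can be stated. The adverse event counts in Appendix A might seem to supply one. They come from an amphotericin plus fluconazole trial that randomized ART timing, with no amphotericin dose contrast, and cannot be read as a dose effect. Confidence is high for the mismatch in the text and low for any bias in practice.

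**What to change.** State deoxycholate 1 mg/kg/day for 7 days as the planned fallback dose in four places: the two synopsis entries, section 4.1 item 4 and section 6.2.1.1. This adopts the wording already in the section 4.1 cohort list and agrees with Tables 2.3 and 6.2. Keep reductions for toxicity and do not class them as protocol deviations.

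Report the number on fallback and the total mg/kg received. Section 7.3 already has daily antifungal administration recorded, and section 13.1 has medications on the Med CRF, so no new data collection is needed.

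Because toxicity reductions can still lower the received dose, add one sensitivity analysis: EFA and hematological and renal toxicity, limited to liposomal participants and controls from the AMBITION liposomal arm.

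The cost is a small loss of planned dosing flexibility, four wording changes and one extra analysis.

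Separately, and as clerical clean-up with no bearing on the dose point, remove the statement in section 6.2.1.1 that additional IV amphotericin is a secondary endpoint. The synopsis and sections 3.2, 11.5 and 11.6 do not list it.
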